Communication and Activation in Pain to
Enhance Relationships and Treat Pain
with Equity (COOPERATE)

NCT03562793

October 1, 2021

Statistical Analysis Plan

D7. STATISTICAL CONSIDERATIONS

D7a. Sample size and power. Our sample size is calculated based on estimated differences of intervention effects between the intervention and control arms on the primary outcome, patient activation (PAM), which is a continuous measure. In [name] pilot study with Veterans with chronic pain,⁸² we found a pre-treatment PAM score of 41.22 (std dev = 5.69) and a post-treatment score of 44.0 (std dev = 5.58), which represents a .49 standard deviation change in patient activation ($d = .49$) in response to a peer intervention for chronic pain. To be conservative, we are powering COOPERATE on a medium effect size of .40. To detect a .40 effect size based on a two-sample independent t-test with type I error =.05 and 80% power, 100 patients per group ($N = 200$) are required. Although our prior pain studies have had low attrition rates (<15%), we will conservatively plan for an attrition rate of 20%, which requires $N = 250$ (200/.80), or 125 patients per group. For secondary outcomes of COOPERATE, we estimated standardized effect sizes (difference in mean change from baseline between treatment groups divided by the pooled SD at baseline) for pain (BPI total) and anxiety (GAD-7) to be .69 and .40, respectively – these estimates were based on data from the SCAMP trial which involved phone-delivered pain self-management.⁹³ In COOPERATE, with a similarly delivered behavioral intervention and a sample size of 100 patients per arm, we will have 98.8% and 59.1% power to detect effect sizes of this magnitude for BPI total and GAD-7 based on a two-sample independent t-test with type I error set at .01 (assuming 5 clinical outcomes adjusted for multiple comparisons with a Šídák adjustment), which provides similar power to our contrast of interest from the linear mixed model. For other secondary outcomes (communication self-efficacy, depression, and pain coping), with a sample size of 200, we have 82.4% power to detect medium effect sizes (.50 SD difference), even after adjusting for multiple comparisons.

D7b. Randomization. Participants will be randomly assigned to one of the two study arms using random numbers generated by our statistician, [name]. Randomization with block sizes of 4 and 8 will be executed to ensure balance.

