All outcomes will be collected at baseline, 3, 6, and 9 months. A linear mixed-model repeated measures approach will be used to test the hypothesis in Aim 1 that COOPERATE will improve the primary outcome of patient activation (PAM) compared to the control condition at the 3-month time point. Fixed effects will include treatment, time (as categorical), and treatment X time interaction. We will examine the associations among the repeated measures within subjects and determine the appropriate variance-covariance structure. Our primary contrast of interest will be the group difference in change from baseline at the 3-month time point. Group differences in change from baseline at other time points (6-month and 9-month) will also be estimated. Covariates found to significantly differ between treatment and control groups at baseline will be included in the models. All analyses will include checking of assumptions and model fit. Working alliance, which is a key indicator of the quality of the patient-provider relationship, will serve as a baseline covariate in all models. Other potential covariates include physical and psychological comorbidities, patient-provider race and gender concordance, and patient-provider relationship length. Since patient activation and number of provider visits could influence one another, we will use number of visits during the prior year as a baseline covariate (if imbalanced between study arms), and will run a sensitivity analysis in which we re-run the final models for primary and secondary outcomes while adjusting for number of visits during the intervention period. Additionally, adherence to the intervention as measured by the number of sessions attended will be assessed for its dose-response effects on the primary and secondary outcomes.

Secondary outcomes of communication self-efficacy, total BPI (as well as BPI subscales: pain intensity and pain interference), and psychological functioning (depression, anxiety, and coping), will all be analyzed with the same mixed model approach as for the primary outcome. Because there are a number of secondary outcomes in Aim 1, we will use the Šídák method to adjust for multiple comparisons.

**Communication and Activation in Pain to
Enhance Relationships and Treat Pain with
Equity (COOPERATE)**

**[name]
Richard L. Roudebush VAMC
[name]
[name]**

Table of Contents:

Study Schema

- 1.0 Background**
- 2.0 Rationale and Specific Aims**

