2.0 Rationale and Specific Aims

COOPERATE focuses on two important, yet frequently neglected, areas for improvement in minority health: patient activation and communication. This is especially important in chronic pain care, since numerous treatment options with a wide range of risks and benefits exist, and since minorities are offered fewer of these pain treatment options. Helping minority Veterans to become more active in their care is critical for improving chronic pain care. This is especially important in light of VA efforts such as the Opioid Safety Initiative, designed to improve safety for Veterans, but which also require engaged, active patients as Veterans must explore alternative pain treatments with their providers—treatments that are feasible for Veterans' individual lifestyles and consistent with their symptom priorities and treatment goals.

COOPERATE (Communication and Activation in Pain to Enhance Relationships and Treat Pain with Equity) is a pragmatic randomized controlled trial of an intervention to improve patient activation and communication with providers for Black Veterans with chronic pain. COOPERATE focuses on 2 essential skill sets necessary to facilitate effective patient activation: 1) goal-setting and prioritization, and 2) communication skills. COOPERATE is delivered over the telephone in 6 sessions (4 weekly sessions followed by 2 booster session) over a period of 12 weeks. The primary study outcome is patient activation.

COOPERATE's specific aims are as follows:

Aim 1: (primary aim). Test the effects of COOPERATE on key Veteran outcomes. We hypothesize that at 3 months (primary end point), 6 months, and 9 months (sustained effects) from baseline, Black Veterans randomized to the COOPERATE intervention will report greater:

- increases in patient activation (primary outcome),

- b) increases in communication self-efficacy,
- c) improvements in pain intensity and interference,
- d) improvements in psychological functioning.

Aim 2: Examine mediating and moderating effects in COOPERATE. We hypothesize that

- a) patient activation will mediate the effect of COOPERATE on clinical outcomes (pain and psychological functioning), and
- b) working alliance will moderate the effect of COOPERATE on patient activation.

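### Improvement, not an error: using step-down Holm-Šídák instead of Šídák on the five powered secondary outcomes raises GAD-7 power from about 59% to about 62%, within the same 5% family-wise error

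*Combined protocol and SAP*

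**What the plan says.** SAP section D7e sets the multiplicity rule for the Aim 1 secondary outcomes: "Because there are a number of secondary outcomes in Aim 1, we will use the" Šídák method. It does not say whether a single-step or a step-down version is meant. Section 8.0 of the protocol gives no multiplicity rule, so D7e is the operative sentence.

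SAP section D7a shows how the adjustment was used in planning. Power is based on a "two-sample independent t-test with type I error set at .01 (assuming 5 clinical outcomes adjusted for multiple comparisons" by Šídák). The results are given as "we will have 98.8% and 59.1% power to detect effect sizes of this magnitude for BPI total and GAD-7", for standardised effects of .69 and .40. The remaining outcomes are covered by this: "For other secondary outcomes (communication self-efficacy, depression, and pain coping), with a sample size of 200, we have 82.4% power" for a .50 SD difference. Together these are five outcomes: BPI total, GAD-7, communication self-efficacy, depression and pain coping. The 100 per arm is the number left after dropout, since "we will conservatively plan for an attrition rate of 20" per cent and 250 are enrolled.

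Two other places affect which tests belong to the family. D7e's outcome list has "total BPI (as well as BPI subscales: pain intensity and pain interference". Section 2.0 of the protocol says "We hypothesize that at 3 months (primary end point), 6 months, and 9 months (sustained effects) from baseline" and includes "improvements in pain intensity and interference" among the hypothesised effects.

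**The concern.** Nothing here is wrong in the sense of invalid. A single-step Šídák rule controls family-wise error at 5%, and D7a's power figures agree with it. The point is that the rule leaves power unused where the plan has least of it. Single-step testing keeps the GAD-7 threshold at about .01 whatever happens to the other outcomes. Yet D7a itself expects BPI total to be rejected almost surely. A step-down rule turns that expected rejection into a looser threshold for the outcomes still to be tested.

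GAD-7 is the outcome with the lowest stated power. Baseline assessments were complete by 10/25/21 (protocol section 5.0, Participant Payments), so adding patients would mean reopening enrolment. A better testing procedure needs none.

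**Working it through.** **Inputs (D7a).** 100 per arm after attrition; effects .69 (BPI total), .40 (GAD-7) and .50 (detectable size for the other three); level .01 for five outcomes. Two-sided testing is assumed, because D7a does not state it; it reproduces D7a's figures.

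**1. Reproduce the plan.** Noncentral t, df = 198, noncentrality d × √(100/2):

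| Effect | Noncentrality | Power at .01 | D7a |
|---|---|---|---|
| .69 | 4.88 | 98.82% | 98.8% |
| .40 | 2.83 | 59.05% | 59.1% |
| .50 | 3.54 | 82.38% | 82.4% |

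The exact Šídák level for five tests is 1 − .95^(1/5) = .01021, which gives 59.33% for GAD-7. Single-step power is therefore about 59% either way.

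**2. Step-down levels.** With k hypotheses still to be tested, the level is 1 − .95^(1/k). For k = 5, 4, 3, 2, 1 this is .0102, .0127, .0170, .0253, .05. Testing runs from the smallest p-value upward and stops at the first failure. The first level equals the single-step level and later levels are looser, so no single-step rejection can be lost.

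**3. Analytic check.** Once BPI total is rejected, GAD-7 faces .01274 at the strictest. Power there is 62.37%.

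**4. Simulation of the full procedure.** Sets of five correlated t statistics with 198 df, at least 400,000 per scenario. Ranges cover between-outcome correlations from 0 to .7:

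| True effects | GAD-7 power, Holm-Šídák |
|---|---|
| GAD-7 .40 only | 59.4-59.6% (no gain) |
| BPI .35, GAD-7 .40 | 60.4-60.8% |
| BPI .69, GAD-7 .40 | about 62.5% |
| as above, other three .30 (assumed) | 65-68% |
| as above, other three .50 (assumed) | 77-78% |

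No single-step rejection was lost in any scenario.

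**5. Size of the gain in patients.** Attrition of 15% instead of 20% would leave 250 × .85 / 2 = 106 per arm. Single-step GAD-7 power is then 62.3% at .01 and 62.6% at .01021. The step-down gain in the two-effect scenario therefore equals about six analysed patients per arm.

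**6. Error control.**
- No true effects: family-wise error is the same for both methods, from 5.0% at correlation 0 to 3.6% at .7.
- BPI total and GAD-7 true: 2.5-3.0% single-step against 3.5-4.5% step-down. At independence the single-step figure is 1 − .95^(3/5) = 3.0%.
- Four true effects (.69, .40, .50, .50): false rejection of the fifth is 1.0% against 3.3-3.9%.

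**7. If both BPI subscales are counted.** The seven-test single-step level is 1 − .95^(1/7) = .0073, with power of 98.4%, 54.8% and 79.4% for effects of .69, .40 and .50. For GAD-7, step-down gives about 57% if the subscales have no effect. It gives 59.7-62.4% if they have assumed effects of .40 to .69 and correlate .80-.85 with the total.

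**The case against.** The arithmetic is not in dispute; the case against is about worth and timing.

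- **Small and conditional.** The gain is three points on one secondary outcome, which still falls well short of 80%. It needs BPI total to be rejected first, on an effect estimated from another trial. The larger gains rest on effects for three outcomes that the plan does not estimate. All of this stands, and it makes the change desirable rather than necessary.
- **Single-step is inferred.** D7e does not exclude a step-down version, and a calculation at .01 could be a conservative first step of one. This also stands. The proposed sentence would then simply remove the ambiguity.
- **The family is the bigger question.** Going from five to seven tests costs GAD-7 59.3 − 54.8 = 4.5 points, more than step-down gains in the main scenario. Section 2.0 also treats clinical outcomes as pain and psychological functioning, so the five in D7a are a reasonable reading rather than a definition. That is a separate decision for the sponsor. Step-down is at least as powerful as single-step within whichever family is chosen.
- **Timing.** The documents show only that some follow-up remained after 10/25/21. At the planned 7-8 enrolments a month, about three months' worth, or 21-24 of 250 participants, would still have been awaiting the 3-month visit. Most 3-month data may therefore already exist, and the documents do not say who has seen them by arm. A late move to an easier rejection rule would carry a credibility cost. This is the most serious limit, and it makes the date of the change a condition of the fix.
- **Trade-offs.** More of the allowed error is used when some effects are real, and step-down testing has no simple simultaneous confidence intervals. A sponsor that values such intervals could reasonably keep single-step.

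**Conclusion.** The point holds as a cheap improvement. For the five outcomes powered in D7a, at the 3-month contrast, Holm-Šídák raises GAD-7 power from about 59% to about 62.5% if BPI total and GAD-7 have the effects D7a estimates and the other three have none. The gain ranges from nil (GAD-7 alone responds) to 1 to 1.5 points (BPI effect halved), and is larger only if the other outcomes also respond. Family-wise error stays within 5%.

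The conclusion assumes two-sided t-tests with 100 analysed per arm as an approximation to the mixed-model contrast, as D7a does. It also assumes that D7e means single-step Šídák. The control described covers one contrast per outcome and does not extend to 6 and 9 months.

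**What to change.** In D7e, replace the reference to Šídák by a sentence specifying step-down Holm-Šídák over BPI total, GAD-7, communication self-efficacy, depression and coping at the 3-month contrast. Give the levels .0102, .0127, .0170, .0253 and .05 in order of p-value. D7a's power figures can then stand as single-step lower bounds for a family of five.

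Date and document the change before anyone examines outcome data by arm. If that has already happened, keep the planned method as primary and show Holm-Šídák as supplementary.

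Whether the BPI subscales and the 6- and 9-month contrasts join the adjusted family is for the sponsor to decide. If both subscales join at 3 months, use seven levels (.0073, .0085, .0102, .0127, .0170, .0253, .05) and restate D7a's single-step power as 98.4%, 54.8% and 79.4%.

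The cost is one SAP sentence, with no change to sample size or data collection, plus the additional error use and the loss of simple simultaneous intervals described above.

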1.0 Background

Chronic pain affects 40-70% of Veterans and amounts to over \$600 billion/year in direct medical costs and lost worker productivity. Racial disparities in pain treatment have been extensively documented. Minority patients, including Veterans, are more likely to be undertreated for pain. Minority Veterans have pain documented less frequently, undergo more urine drug tests, and are more likely to be referred for substance abuse evaluation than White Veterans. Compounding these pain care disparities, minority Veterans exhibit lower levels of patient activation than Whites. Patient activation—having knowledge, confidence, and skills to manage health—is associated with better health experiences, self-management, and outcomes. Low activation is frequently manifested in poorer communication among minority patients. Minority patients are less likely to share their concerns with providers, ask questions, and prepare for their clinic visits. This poor communication is associated with lower quality care, poorer patient-provider relationships, and treatment non-adherence. The poorer communication experienced by minorities is exacerbated by the documented difficulties in patient-provider communication about chronic pain and its treatment—particularly where opioids are concerned.

2.0 Rationale and Specific Aims

COOPERATE focuses on two important, yet frequently neglected, areas for improvement in minority health: patient activation and communication. This is especially important in chronic pain care, since numerous treatment options with a wide range of risks and benefits exist, and since minorities are offered fewer of these pain treatment options. Helping minority Veterans to become more active in their care is critical for improving chronic pain care. This is especially important in light of VA efforts such as the Opioid Safety Initiative, designed to improve safety for Veterans, but which also require engaged, active patients as Veterans must explore alternative pain treatments with their providers—treatments that are feasible for Veterans' individual lifestyles and consistent with their symptom priorities and treatment goals.

COOPERATE (Communication and Activation in Pain to Enhance Relationships and Treat Pain with Equity) is a pragmatic randomized controlled trial of an intervention to improve patient activation and communication with providers for Black Veterans with chronic pain. COOPERATE focuses on 2 essential skill sets necessary to facilitate effective patient activation: 1) goal-setting and prioritization, and 2) communication skills. COOPERATE is delivered over the telephone in 6 sessions (4 weekly sessions followed by 2 booster session) over a period of 12 weeks. The primary study outcome is patient activation.

COOPERATE's specific aims are as follows:

Aim 1: (primary aim). Test the effects of COOPERATE on key Veteran outcomes. We hypothesize that at 3 months (primary end point), 6 months, and 9 months (sustained effects) from baseline, Black Veterans randomized to the COOPERATE intervention will report greater:

- increases in patient activation (primary outcome),

- b) increases in communication self-efficacy,
- c) improvements in pain intensity and interference,
- d) improvements in psychological functioning.

Aim 2: Examine mediating and moderating effects in COOPERATE. We hypothesize that

- a) patient activation will mediate the effect of COOPERATE on clinical outcomes (pain and psychological functioning), and
- b) working alliance will moderate the effect of COOPERATE on patient activation.

Aim 3: (pre-implementation aim). Understand facilitators and barriers to implementing COOPERATE. Using the RE-AIM framework, we will conduct qualitative interviews with a purposefully selected subsample of intervention Veterans and with clinicians to better prepare for implementing COOPERATE.

3.0 Inclusion/Exclusion Criteria

Participants will include 250 Black Veterans who are receiving medical care from the Veterans Health Administration.

Eligible patients must:

- 1) be Black or African American;
- 2) have musculoskeletal pain in the low back, cervical spine, or extremities (hip, knee, shoulder) for greater than 3 months.

Patients will be excluded if electronic medical records indicate:

- 1) a psychotic disorder diagnosis
- 2) current substance use disorder
- 3) severe medical conditions precluding participation (e.g., NY Heart Association Class III or IV heart failure), or if the eligibility screener reveals
- 4) active suicidal ideation
- 5) severe hearing/speech impairment

4.0 Enrollment/Randomization

Enrollment

Our center's data management group will run a query in CPRS (Computerized Patient Record System) to identify potentially eligible patients, who will be recruited from 9 clinics: Roudebush VAMC's 5 primary care clinics, the Indy West Clinic, and the 3 Community-Based Outpatient Clinics (CBOCs) at Bloomington, Martinsville, and Terre Haute. Black Veterans with musculoskeletal pain will be identified. We will use ICD-10 codes from our prior work to identify these conditions.

Alternatively, using Corporate Data Warehouse (CDW), we will identify potentially eligible patients from the 9 clinics: Roudebush VAMC's 5 primary care clinics, the Indy West Clinic and the 3 Community-Based Outpatient Clinics (CBOCs) at Bloomington, Martinsville, and Terre Haute. Black Veterans with musculoskeletal pain will be

identified. We will use ICD-10 codes from our prior work to identify these conditions. The Corporate Data Warehouse is located on VINCI servers and will be accessed using the DART request process.

This list of potential participants will be updated monthly during the enrollment period, and a recruitment letter, describing the study will be mailed to qualifying Veterans. Potential participants will be contacted by phone within a week after mailing the letter to assess eligibility (including confirmation of musculoskeletal pain and race) and determine their interest in participating. If the Veteran is eligible and interested, an appointment will be scheduled at the Roudebush VAMC to obtain a signed informed consent statement and HIPAA authorization or the consent will take place by phone and the consent forms will be mailed. Backup recruitment methods include 1) giving Veterans opportunities to self-refer by responding to study advertisements placed in hospital elevators and clinics, and 2) contacting potential participants in clinics by cross-referencing the CPRS list with the weekly appointment roster for each participating VA provider.

Due to the COVID-19 pandemic, if the Veteran is unable to consent in-person they will be mailed an ICF and allowed time to review it. COOPERATE research staff will follow-up with each Veteran to answer questions about the ICF and get verbal consent to participate in the study. Once the COVID-19 social distancing/quarantine procedures are lifted, we will return to normal in-person consenting procedures with written signatures.

For clinicians, COOPERATE research staff will present the study at regularly scheduled clinic meetings. Clinicians in attendance will be provided an Interest in Participation slip to indicate, via checkbox, whether they are or are not interested in participating. Those not interested in participating will be removed from the recruitment list. The research team will then email the Study Information Sheet to all clinicians interested in participating and those not present at the clinic meeting. The research team will respond to incoming emails and/or follow-up in person accordingly. Clinicians choosing to participate in the study will be scheduled for interviews at the Roudebush VAMC, at which time the research team will review the Study Information Sheet and ask for questions or concerns and offer a paper copy or additional email copy prior to participation.

Randomization

Participants will be randomly assigned to one of the two study arms using random numbers generated by our statistician. Randomization with block sizes of 4 and 8 will be executed to ensure balance.

